## 7.2. STATISTICAL ANALYSES

- SAS software version 9.4 (SAS Institute Inc. NC, USA) will be used for the analysis.
- For primary effectiveness analysis and primary safety analysis (see 5.1 and 5.2), statistical tests will be performed at  $p=0.05$  (two-sided) with no adjustment for multiplicity. P values less than 0.05 will be regarded as statistically significant.
- We will conduct multiple secondary analysis as shown below and these repetitive statistical analyses may cause the "Multiple Testing Problem". Here these multiple analyses will be concluded only as an exploratory purpose and we do not intend to conclude anything from the results obtained from sub-endpoint analyses here. No multiple testing adjustment will be taken.

### 7.2.1. Sensitivity analysis

E-values (evidence for causality) will be calculated for the primary effectiveness and safety analysis from calculated hazard ratios and 95% confident intervals to estimate the extent of unmeasured confounding. In this study, the E-value is defined as the minimum strength of association on the calculated hazard ratio and the limit of the confidence interval closest to the null in the primary effectiveness and safety analysis.

### 7.2.2. Power calculation

The randomized clinical trial, ARISTOTLE study, has revealed that hazard ratios of apixaban to warfarin in patients with a previous history of stroke/TIA are almost similar to those without a history of stroke/TIA ( $p$  for interaction : 0.71). The hazard ratio for Stroke/SE in the previous Japanese comparison of Apixaban and warfarin using the MDV database that will be used in this study was 0.65. Based on these two results, we can estimate that the hazard ratio in the current secondary prevention patients is also about 0.65. All statistical tests will be performed at  $p=0.05$  (two-sided) with no adjustment for multiplicity.

The following sample size calculation will be based on the significance level of 0.05 (two-sided) and power of 80%.Desired Power	Hazard Ratio	Event Rate (Control)	Required Sample Size per Group
0.8	0.6	1.2 %/year	3,166
		1.6 %/year	2,378
		2.1 %/year	1,815
		2.6 %/year	1,469
	0.7	1.2 %/year	6,083
		1.6 %/year	4,570
		2.1 %/year	3,488
		2.6 %/year	2,823
	0.8	1.2 %/year	14,683
		1.6 %/year	11,031
		2.1 %/year	8,422
		2.6 %/year	6,817

In the preliminary study, we have found that more than 15,000 secondary prevention patients with NVAF who take apixaban or warfarin.

So, probably the power may be higher than 0.8 in this study.

### 7.2.3. Summary of Analyses

All analysis other than patient characteristics will be conducted as a two-sided p-value less than 0.05.

Patient characteristics will be compared using standardized difference as a cut-off value of 0.1.

Outcome/items to be examined	Analysis Cohort	Supports Protocol Objective Number	Subgroup	Statistical Method	Covariates/Strata	Missing Data

PFIZER CONFIDENTIAL

Patients characteristics	Cohorts in Step 1 and Step 2		None	unpaired t-test or Mann-Whitney U-test, categorical variables: chi-square test		No imputation
The incidence rates of stroke/SE and major bleeding per 1,000 person-years	Cohorts in Step 1 and Step 2		None	1000 person-years	Refer to section 5.4	No imputation
Interaction analysis	Cohorts in Step 1 and Step 2		None	Cox proportional hazards regression model	Warfarin/apixaban, primary/secondary	No imputation
Incidence rate of a composite of recurrent stroke (ischemic and hemorrhagic)/SE (primary effectiveness analysis)	Balanced cohorts	Effectiveness 1	None	1000 person-years	Refer to section 5.4	No imputation
Incidence of cardiogenic cerebral embolism (secondary effectiveness endpoint)	Balanced cohorts	Effectiveness 1	None	1000 person-years	Refer to section 5.4	No imputation
Incidence of cerebral infarction (secondary effectiveness endpoint)	Balanced cohorts	Effectiveness 1	None	1000 person-years	Refer to section 5.4	No imputation
Incidence rate of major bleeding (primary safety endpoint)	Balanced cohorts	Safety 1	None	1000 person-years	Refer to section 5.4	No imputation
Incidence rate of intracranial hemorrhage (secondary safety endpoint)	Balanced cohorts	Safety 1	None	1000 person-years	Refer to section 5.4	No imputation
Incidence rate of gastrointestinal bleeding (secondary safety endpoint)	Balanced cohorts	Safety 1	None	1000 person-years	Refer to section 5.4	No imputation
Incidence of rate of intraocular bleeding (secondary safety endpoint)	Balanced cohorts	Safety 1	None	1000 person-years	Refer to section 5.4	No imputation
Time course of proportion of a composite of the incidence of recurrent stroke (ischemic and hemorrhagic)/SE -free NVAF patients treated with warfarin or apixaban	Balanced cohorts	Effectiveness 2	None	Kaplan Meier curves	Refer to section 5.4	No imputation

PFIZER CONFIDENTIAL

Time course of proportion recurrent cardiogenic cerebral embolism-free NVAF patients treated with warfarin or apixaban	Balanced cohorts	Effectivess 2	None	Kaplan Meier curves	Refer to section 5.4	No imputation
Time course of proportion of recurrent cerebral infarction-free NVAF patients treated with warfarin or apixaban	Balanced cohorts	Effectivess 2	None	Kaplan Meier curves	Refer to section 5.4	No imputation
Time course of proportion of major-free NVAF patients treated with warfarin or apixaban	Balanced cohorts	Safety 2	None	Kaplan Meier curves	Refer to section 5.4	No imputation
Time course of proportion of intracranial hemorrhage-free NVAF patients treated with warfarin or apixaban	Balanced cohorts	Safety 2	None	Kaplan Meier curves	Refer to section 5.4	No imputation
Time course of proportion of gastrointestinal bleeding-free NVAF patients treated with warfarin or apixaban	Balanced cohorts	Safety 2	None	Kaplan Meier curves	Refer to section 5.4	No imputation
Time course of proportion of intraocular bleeding-free NVAF patients treated with warfarin or apixaban	Balanced cohorts	Safety 2	None	Kaplan Meier curves	Refer to section 5.4	No imputation
Risk of a composite of recurrent stroke (ischemic and hemorrhagic)/SE during the follow-up period in NVAF patients treated with warfarin or apixaban	Balanced cohorts	Effectivess 3	None	Cox proportional hazards regression model	Refer to section 5.4	No imputation
Risk of recurrent cardioembolic stroke during the follow-up period in NVAF patients treated with warfarin or apixaban	Balanced cohorts	Effectivess 3	None	Cox proportional hazards regression model	Refer to section 5.4	No imputation
Risk of recurrent cerebral infarction during the follow-up period in NVAF patients treated with warfarin or apixaban	Balanced cohorts	Effectivess 3	None	Cox proportional hazards regression model	Refer to section 5.4	No imputation
Risk of major bleeding in patients treated with apixaban compared to that in patients treated with warfarin	Balanced cohorts	Safety 3	None	Cox proportional hazards regression model	Refer to section 5.4	No imputation

PFIZER CONFIDENTIAL

Risk of intracranial hemorrhage in patients treated with apixaban compared to that in patients treated with warfarin	Balanced cohorts	Safety 3	None	Cox proportional hazards regression model	Refer to section 5.4	No imputation
Risk of gastrointestinal tract bleeding in patients treated with apixaban compared to that in patients treated with warfarin	Balanced cohorts	Safety 3	None	Cox proportional hazards regression model	Refer to section 5.4	No imputation
Risk of intraocular bleeding in patients treated with apixaban compared to that in patients treated with warfarin	Balanced cohorts	Safety 3	None	Cox proportional hazards regression model	Refer to section 5.4	No imputation

PFIZER CONFIDENTIAL

[figure not shown]
[figure not shown]

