- Balanced (after IPTW) patient clinical and demographic characteristics will be shown. Covariate balance between apixaban and warfarin cohorts after s-IPTW will be assessed in terms of the standardized differences with a threshold of 0.1.
- Kaplan Meier curves of balanced cohorts for each endpoint will be drawn.
- Incidence rates of endpoints will be calculated and shown per 1000 person-year.
- Hazard ratios with 95% confidence intervals will be calculated using a Cox proportional hazards regression model that incorporate only the index OACs as independent variables.

Milestones :

- Data extraction start: Apr 15, 2022
- End of data extraction: Jun 30, 2022
- Final report approval: Aug 30, 2022

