8.7. Data analysis

The detailed methodology for data analysis will be described in the Statistical Analysis Plan (SAP).

As a first step, extracted patients will be divided into two cohorts, primary prevention cohort and secondary prevention cohort based on the previous diagnosis of stroke. Clinical and demographic characteristics will be compared with two cohorts at baseline and on the index date (date of the initiation of warfarin and apixaban) and incidence rates of stroke/SE and major bleeding per 1,000 person-years will be calculated during follow-up period. In addition, interaction analysis will be conducted to investigate an interaction between OAC (warfarin/apixaban) and presence or absence of the previous episode of stroke.

- As a second step, only secondary prevention cohort will be used for further analyses as follows, Crude (before IPTW) patient characteristics are compared between warfarin and apixaban cohorts using appropriate methods (continuous variables: unpaired t-test or Mann-Whitney U-test, categorical variables: chi-square test)
- A propensity score is calculated based on multinomial logistic regressions in order to account for confounding effects and to ensure that patient characteristics are balanced between the warfarin cohort and apixaban cohort. An inverse probability of treatment weighting (IPTW) method using the calculated propensity score will be applied. To avoid sample size inflation and to ensure appropriate estimation of variances, s-IPTW (stabilized IPTW) is used here.
- Balanced (after IPTW) patient clinical and demographic characteristics are shown. Covariate balance between apixaban and warfarin cohorts after s-IPTW is assessed in terms of the standardized differences with a threshold of 0.1
- Kaplan Meier curves of balanced cohorts for each endpoint are drawn.
- Incidence rates of endpoints are calculated and shown per 1000 person-years.
- Hazard ratios with 95% confidence intervals will be calculated using a Cox proportional hazards regression model that incorporate only the index OACs as independent variables.

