## 5. ENDPOINTS AND COVARIATES

### 5.1. EFFICACY/EFFECTIVENESS ENDPOINT(S)

#### 5.1.1. Primary effectiveness endpoint and primary analyses

The following outcomes will be assessed as effectiveness endpoints. Primary endpoint is incidence of a composite of recurrent stroke (ischemic and hemorrhagic stroke)/SE in NVAF patients treated with warfarin or apixaban. The definition of “recurrent” is as follows, “once patients discharge from the hospital and become outpatients and then rehospitalized due to stroke (major reason for the hospitalization is stroke described in the DPC admission information)

[figure not shown]
[figure not shown]
1. Incidence rate (per 1,000 person-years) of a composite of recurrent stroke (ischemic and hemorrhagic stroke)/SE during the follow-up period in NVAF patients treated with warfarin or apixaban
2. Time course of proportion of the incidence of a composite of recurrent stroke (ischemic and hemorrhagic stroke)/SE-free NVAF patients treated with warfarin or apixaban (shown as two Kaplan-Meier curves, for warfarin cohort and apixaban cohort, which will be statistically compared by a Log-rank test).
3. Risk of a composite of recurrent stroke (ischemic and hemorrhagic stroke)/SE in patients treated with apixaban compared to that in patients treated with warfarin. Hazard ratio and 95% confident intervals will be calculated by a COX proportional hazard method

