### 5.4. COVARIATES

Variable	Role	Operational definition
Previous stroke		
Previous incidence of stroke	Patient characteristic:	
Previous incidence of TIA	Patient characteristic:	Defined elsewhere using ICD-10 codes

PFIZER CONFIDENTIAL

Types of previous stroke	Patient characteristic:	cardioembolic stroke or cerebral infarction
Treatment status	Patient characteristic:	Inpatients or outpatients
Hospitalization days	Patient characteristic:	0 or days in hospital
NVAF diagnosis and treatment		
Year	Patient characteristic	Year first diagnosed with NVAF
Anticoagulant	Patient characteristic	Warfarin or apixaban
Patients		
age	Patient characteristics on index date	Years
Age category	Patient characteristics on index date	
age $\leq 65$		
age $65 < , \leq 75$		
age $75 <$		
Gender category	Patient characteristics on index date	Male or female
Body weight	Baseline characteristic	Kg (if available)
Height	Baseline characteristic	cm (if available)
BMI	Baseline characteristic	Calculated from body weight and height using a formula of (weight [kg]) / (height [m]) 
Comorbidity profile		
Chronic obstructive pulmonary disease (COPD)	Baseline characteristic	Defined elsewhere using ICD-10 codes
Congestive heart disease	Baseline characteristic	Defined elsewhere using ICD-10 codes
Ischemic heart/coronary artery disease	Baseline characteristic	Defined elsewhere using ICD-10 codes
Diabetes	Baseline characteristic	Defined elsewhere using ICD-10 codes
Hyperlipidemia	Baseline characteristic	Defined elsewhere using ICD-10 codes
Hypertension	Baseline characteristic	Defined elsewhere using ICD-10 codes
Liver disease	Baseline characteristic	Defined elsewhere using ICD-10 codes
Renal disease	Baseline characteristic	Defined elsewhere using ICD-10 codes
Peripheral vascular disease	Baseline characteristic	Defined elsewhere using ICD-10 codes
Pregnancy	Exclusion criteria	Presence of "pregnancy"-related ICD-10 codes.

PFIZER CONFIDENTIAL

Cancer	Baseline characteristic	Defined elsewhere using ICD-10 codes
VTE	Baseline characteristic (exclusion criteria)	Defined elsewhere using ICD-10 codes
Medicines		
Anti-hypertensive drugs	Baseline characteristic	Defined elsewhere using drug codes
Anti-platelet drugs	Baseline characteristic	Defined elsewhere using drug codes
NSAIDs (chronic use*)	Baseline characteristic	Defined elsewhere using drug codes
Statins	Baseline characteristic	Defined elsewhere using drug codes
Outcomes		

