#### 7.1.2. Patient characteristic balancing

[figure not shown]
In this study, matched cohorts (warfarin cohort versus apixaban cohort) will be created. A propensity score will be calculated based on multivariable logistic regressions in order to account for confounding effects\* and to ensure that patient characteristics will be balanced between the warfarin cohort and apixaban cohort. An inverse probability of treatment weighting (IPTW) method using the calculated propensity score will be applied. To avoid sample size inflation and to ensure appropriate estimation of variances, s-IPTW (stabilized IPTW) is used here.

Balanced (after IPTW) patient clinical and demographic characteristics will be shown. Covariate balance between apixaban and warfarin cohorts after s-IPTW will be assessed in terms of the standardized differences with a threshold of 0.1. We will present the data for each variables and standardized differences in the same table side by side to ensure that two cohorts are balanced after IPTW.

\* Covariates used for the calculation of propensity score

- Gender: male or female
- Age: absolute years
- BMI: categories BMI (kg/m^2) (<18, 18 to <22, 22 to <25, 25+, missing)
- CHADS2 score: absolute score, categories (0, 1, 2, 3, 4, 5, 6)

PFIZER CONFIDENTIAL

[figure not shown]

- CHA2DS2-VASc: absolute score, categories (0, 1, 2, 3, 4, 5, 6, 7, 8, 9)
- Treatment status of the most recent stroke before the index date (outpatient treatment, inpatient treatment, missing)
- mRS (modified Rankin Scale) at time of admission due to most recent stroke (0,1,2,3,4,5, missing)
- JCS (Japan coma scale) at time of admission due to most recent stroke (I, II, III, missing)
- ADL (Activities of daily living) at time of admission due to most recent stroke (0-19, 20-39, 40-59, 60-79, 80-100, missing)
- Duration of hospitalization due to most recent stroke
- Destination after discharge from hospitalization due to most recent stroke (1 or 5 or other (2,3,4,6,7,8,9))
- Use of tPA or urokinase for treatment of most recent ischemic stroke (thrombolytic therapy)
- Type of most recent stroke stroke (TIA, ischemic stroke, cerebral bleeding, cardiogenic thromboembolism, unknown/others)
- 

*Note: in patients with a medical history of incidence multiple stroke events, only information regarding most recent stroke (i.e., stroke event closest to the index date) will be used.*

- Comorbidities
  - Hypertension
  - Heart failure in baseline

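### The SAP summary table points the primary Cox models to section 5.4, which conflicts with the protocol's OAC-only model and cannot be used as a covariate list; four baseline variables in 5.4 are also missing from the propensity list

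*SAP*

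**What the plan says.** **Protocol.** Section 8.7 specifies, after stabilized weighting, a "Cox proportional hazards regression model that incorporate only the index OACs as independent variables". The abstract (section 3) gives the same rule. Section 8.7 leaves detailed methodology to the SAP.

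**SAP text.** Section 2.1 describes weighting and then a Cox analysis on the balanced cohorts. Section 5.1.1 says only that "Hazard ratio and 95% confident intervals will be calculated by a COX proportional hazard method", and 5.2.1 says the same for major bleeding. Neither names the model terms.

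**SAP table.** In section 7.2.3, the Cox rows for both primary endpoints have "Refer to section 5.4" under Covariates/Strata and state that missing data are not imputed. The interaction row uses the same column to list its terms: "Warfarin/apixaban, primary/secondary".

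**The two lists.** Section 5.4 is a table of all study variables. It includes weight as "Kg (if available"), height on the same terms, and "Year first diagnosed with NVAF". Section 7.1.2 has its own list, headed "Covariates used for the calculation of propensity score".

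**The concern.** A programmer working from the SAP, to which the protocol defers, finds one instruction on Cox covariates, and it does not match the protocol. The two specifications estimate different things. A weighted Cox model with treatment alone gives a marginal hazard ratio in the weighted cohort. Adding covariates gives a conditional hazard ratio, and if weight and height were required without imputation it might be fitted in fewer patients. Both primary analyses are tested at two-sided 0.05 (SAP 7.2), so the model has to be fixed before either result is seen.

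The OAC-only model has a further consequence: all confounding control then rests on the propensity list in 7.1.2. A baseline variable that the study collects but leaves off that list is not adjusted for in any analysis.

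**Working it through.** **1. Can section 5.4 serve as a covariate list?** Its contents by role:

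| Content of SAP 5.4 | Usable as a Cox covariate? |
|---|---|
| Baseline characteristics, comorbidities, medicines | Yes |
| Anticoagulant | No, it is the exposure |
| Pregnancy, VTE | No, they carry an exclusion role |
| Ischemic and hemorrhagic stroke, systemic embolism, major, intracranial, gastrointestinal and intraocular bleeding | No, they are outcomes |
| Weight and height if available; BMI derived from them | Only with a rule for missing values, which the Cox rows lack |

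Taken literally, the entry cannot be programmed.

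**2. Is it the weighting list?** No.

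- Only in 5.4: year of NVAF diagnosis, COPD, hyperlipidemia, statins, separate weight and height, pregnancy, VTE.
- Only in 7.1.2: CHADS2, CHA2DS2-VASc, mRS, JCS, ADL, discharge destination, thrombolysis, history of myocardial infarction, hyperthyroidism, dementia, gastrointestinal ulcer, history of bleeding, anti-arrhythmics, beta-blockers, heparins, cardioversion, ablation.
- BMI has a missing category in 7.1.2.

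Setting aside the exclusion variables, and weight and height (represented by BMI), four baseline variables drop out of the weighting: year of diagnosis, COPD, hyperlipidemia and statins.

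**3. Does the sample-size table indicate which model is meant?** It reproduces. Schoenfeld events are 4(1.960 + 0.842)²/(ln HR)², which gives 121, 247 and 631 for HR 0.6, 0.7 and 0.8. N per group is events divided by (p₁ + p₂), with p₁ = 1 − (1 − r)² and p₂ = 1 − (1 − r)^(2·HR), meaning two full years of follow-up.

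- HR 0.6, 1.2%/year: 121/(0.023856 + 0.014383) = 3,165 (SAP 3,166)
- HR 0.7, 1.6%/year: 247/(0.031744 + 0.022328) = 4,568 (SAP 4,570)
- HR 0.8, 2.6%/year: 631/(0.051324 + 0.041274) = 6,815 (SAP 6,817)

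This is a two-group comparison with no covariate terms. It fits an OAC-only model but settles nothing about the Cox rows.

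**4. What could a complete-case model cost?** The documents give no missing fraction, so this is illustration only. From SAP 7.2.2: 15,000 patients in total, HR 0.65, the four control rates. Assumed: 7,500 per arm, one or two years of follow-up for everyone, and 10%, 30% or 50% of events lost.

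Events D = 7,500 × [(1 − e^(−rt)) + (1 − e^(−0.65rt))]; power = Φ(√(D/4) × |ln 0.65| − 1.96). For r = 0.012 and t = 2, D = 294 and power = Φ(8.573 × 0.4308 − 1.96) = 96%. With 30% lost, D = 206 and power is 87%.

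| Years | Control rate | Events | No loss | 10% lost | 30% lost | 50% lost |
|---|---|---|---|---|---|---|
| 2 | 1.2% | 294 | 96% | 94% | 87% | 74% |
| 2 | 1.6% | 391 | 99% | 98% | 94% | 85% |
| 2 | 2.1% | 510 | >99% | >99% | 98% | 93% |
| 2 | 2.6% | 629 | >99% | >99% | >99% | 97% |
| 1 | 1.2% | 148 | 74% | 70% | 59% | 46% |
| 1 | 1.6% | 197 | 86% | 82% | 71% | 57% |
| 1 | 2.1% | 258 | 93% | 91% | 82% | 69% |
| 1 | 2.6% | 318 | 97% | 95% | 90% | 78% |

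The result depends almost wholly on the assumptions. With 30% lost, power stays above 80% at 2.1 and 2.6%/year for either follow-up. It falls below 80% at 1.2 and 1.6%/year with one year of follow-up.

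**The case against.** The strongest reply is that the table entry is boilerplate. The same words fill the incidence-rate and Kaplan-Meier rows, where model covariates have no clear meaning. Section 5.4 nearly repeats the protocol's Table 1, so it reads as a list of definitions, and the outcomes in it suggest that nobody meant it as a list of regressors. No SAP sentence mentions an adjusted or multivariable Cox model, and the protocol states the OAC-only rule twice.

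Most of this stands. A reader might infer that the SAP commits the primary analysis to a 5.4-adjusted hazard ratio in patients with recorded weight and height. The documents do not support that. Adjustment is read from a table cell, and complete-case analysis is a second inference on top of it: no imputation is compatible with a missing category such as 7.1.2 gives BMI.

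The reply does not remove the point. The interaction row shows that the column can name model terms, and the SAP text is silent on the terms for the primary models. Even a generic pointer leads to the wrong place, because the covariates that matter for the weighted analysis are in 7.1.2.

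On the four omitted variables, it is fair to say that no bias has been shown for any of them and that they raise a separate question from the Cox conflict. It is also fair that calendar year could produce large weights if drug choice shifted over time. That is a reason to check overlap. It does not justify leaving the four out without comment.

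**Conclusion.** The point holds in two parts.

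1. Protocol and SAP do not state the same primary Cox model. The SAP entry is unusable if taken literally and ambiguous if it is a pointer, and nothing in the SAP decides between the readings. This rests on the texts alone.
2. Year of NVAF diagnosis, COPD, hyperlipidemia and statins are listed as baseline variables but are outside the propensity list, so an OAC-only model leaves them unadjusted. With inclusion from 2008 through 2021 (SAP 4.1.1), calendar year is an obvious candidate confounder. The direction and size of any bias cannot be derived from the documents.

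A loss of power should not be claimed. It would need the literal reading, a complete-case rule and a missing fraction, and the documents establish none of these. The point should be corrected before any hazard ratio is seen.

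**What to change.** - In the Cox rows of SAP 7.2.3 for the balanced cohorts, replace the pointer to 5.4 with: *index OAC only, stabilized-IPTW weighted using the 7.1.2 covariates, robust variance*. This restores the protocol's model and names a variance method, which the SAP does not.
- Add year of NVAF diagnosis, COPD, hyperlipidemia and statins to the list in 7.1.2. Report propensity overlap and the distribution of the weights.
- SAP 7.1.2 sets a 0.1 threshold for standardized differences but no consequence for exceeding it. State that any covariate still above 0.1 after weighting is added to the weighted Cox model only in a labelled sensitivity analysis. Adding it to the primary model would again depart from the protocol's rule, "that incorporate only the index OACs as independent variables".

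The cost is SAP wording and a somewhat larger propensity model; the variables are already on the study's variable list. The small downside is somewhat more variable weights, mainly from calendar year, which the overlap check would show.
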